7. STUDY POPULATION

Subject disposition information for the total analysis dataset will be generated. Descriptive statistics will be generated in summary tables comparing the active treatment and placebo groups across demography, baseline MQT results, comorbid allergic asthma, duration of Mountain Cedar pollen allergy, number of baseline concomitant medications for the ITT, MITT, PP, and Safety datasets. Nominal variables will be described by number and percentages of patients in each category. Quantitative variables will be described using means, standard deviations and percentiles, as appropriate. Number and percentage of missing values will be tabulated and reported, as appropriate.

7.1. Subject Disposition

Subject disposition from screening, enrollment, treatment, thru to drop-out or completion will be presented in tabular format. Subject enrollment start and end dates will be reported by site.

8.2 Protocol Violations

A listing of protocol deviations/violations will be produced.

8.3 Demographic Characteristics

Demographic variables (e.g., sex, age, ethnic origin, and race) will be summarized by descriptive statistics (count and percentage only) using tabular format.

8.4 Medical History

Patients with other allergies by group and with controlled asthma by group will be summarized in tabular format. Clinically significant medical history will be reported by group and organ system.

8.5 Physical Exam

Clinically significant findings on physical exams before and after completion of the study will be reported in tabular format by organ system.

Statistical Analysis Plan

8.6 Treatment Compliance

Listing of patients by treatment visit with dates and windows will be produced.

9. EFFICACY ANALYSIS

9.1 Primary Efficacy Analysis

Objective: To evaluate the efficacy of ILIT relative to placebo during the 2018-2019 Texas Mountain Cedar allergy season as assessed by the daily total combined score (TCS), a composite of the Daily Symptoms Score (DSS) and Daily Medication Score (DMS).

Endpoint: Average daily TCS during the 2018-2019 Mountain Cedar pollen season

Population: The per protocol dataset, which includes participants who received three study treatment injections and completed at least 50% of expected electronic diary responses during the allergy season, with no major protocol violations.

Analysis Period: The analysis period will be peak mountain cedar pollen season in the local area, defined as the period when the first cedar pollen count was above 100 ppm to the last date pollen was above 100 ppm followed by more than five (5) consecutive days with a count below 100 ppm.

Statistical Testing Method and Considerations: The TCS is a repeated measure, but statistical comparisons were between group average TCS scores during peak season. Between group comparisons will be made using either ANOVA, a parametric test, if the underlying data distribution supports use of parametric testing, otherwise the comparison will be made using a non-parametric test, the Kruskal-Wallis test, based on rank order.

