## 7 STUDY INTERVENTION DISCONTINUATION AND PARTICIPANT DISCONTINUATION/WITHDRAWAL

### 7.1 DISCONTINUATION OF STUDY INTERVENTION

Participants may choose to discontinue ILIT treatment at any time without prejudice. Discontinuing participation in the study will not preclude patients from continuing alternate allergy treatments. Patients may choose to continue as a patient of TASC or seek treatment elsewhere at their own expense. Discontinuation of ILIT treatment does not mean discontinuation from the study, and remaining study procedures should be completed as indicated by the study protocol to ensure patient follow-up through the end of the allergy season. Reasonable efforts will be made to contact the patient to encourage orderly completion of study discontinuation procedures. If a clinically significant finding is identified (including, but not limited to new medical conditions, adverse effects, or worsening of symptoms) after enrollment, the investigator or qualified designee will determine if any change in clinical patient management is needed. New clinically relevant finding will be reported as an adverse event (AE). For patients that discontinue the study prior to the scheduled end-of-study visit, the reason for discontinuation will be collected.

The data to be collected at the time of discontinuation will include the following:

- Adverse events, concomitant medications, reasons for discontinuation, vital signs

ILIT treatment of subjects may be discontinued at any time by the investigator any at any time the investigator determine that it is clinically a clinical determination that it is in the interest of the patient to discontinue treatment.

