#### 8.1.1.5 Patient Diary

During the allergy season, patients will receive a daily diary with a series of numeric questions to be answered electronically for measurement of the daily symptom and daily medication score, including use of a rescue inhaler for patients with asthma. Patients will be considered compliance if they complete at least 50% of expected daily responses. Patients will receive reminders from the EDC system via text message or email, as well as general outreach from TASC regarding their AIT journey.

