## 9.3 POPULATIONS FOR ANALYSES

- Intent-to-Treat (ITT) Analysis Dataset: will include all randomized participants and be used for subject listings and demographics tables.
- Modified Intention-to-Treat (MITT) Analysis Dataset: will include all participants who received at least one (1) study intervention and completed at least one (1) complete daily e-diary assessment and be used for production of efficacy tables, subject listings, and demographics tables.
- Safety Analysis Dataset: will include all participants who took received at least one (1) dose of study intervention regardless of whether they provided any diary data and will be used for safety tables and tolerability tables.
- Per-Protocol (PP) Analysis Dataset: will include the subset of participants in the MITT data set who received three study treatment injections and completed at least 50% of e-diary responses during the allergy season (follow-up period), and has no other major protocol violations, and will be used for production of supplementary efficacy tables and analyses.
- Additional datasets for sub-population will include the adjusted ITT, MITT, Safety Dataset, and PP dataset for the subset of patients with asthma at baseline.

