6. ANALYSIS POPULATIONS

The populations as defined below were used in study summaries and analyses.

Intent-to-Treat (ITT) Analysis Dataset: will include all consented participants and be used for subject listings and demographics tables.

Modified Intention-to-Treat (MITT) Analysis Dataset: will include all consented participants who received at least one (1) study intervention (intralymphatic injection) and completed at least one (1) complete daily e-diary assessment and be used for production of efficacy tables, subject listings, and demographics tables.

Safety Analysis Dataset: will include all participants who took received at least one (1) dose of study intervention (intralymphatic injection) regardless of whether they provided any diary data and will be used for safety tables and tolerability tables.

Per-Protocol (PP) Analysis Dataset: will include the subset of participants in the MITT data set who received three study treatment injections and completed at least one e-diary responses during the allergy season (defined below), and had no other major protocol violations, and will be used for production of supplementary efficacy tables and analyses.

Additional exploratory datasets for sub-populations and post hoc analysis will include the adjusted per protocol dataset (aPP-IgE) for baseline serum IgE, which is the PP dataset subset of patients with baseline levels of mountain cedar-specific serum IgE greater than 0.3 (definitively positive) and the aPP subset for controlled asthma (aPP-A), if there are sufficient numbers of patients with confirmed, controlled asthma at baseline.

The mountain cedar pollen season will be defined from the first date of a mountain cedar pollen count greater than or equal to 100 ppm thru the date with a pollen

Statistical Analysis Plan

count greater than or equal to 100 ppm followed by five consecutive days with a pollen count below 100 ppm during the Winter 2018-2019 mountain cedar pollen season in Central Texas.

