9.2 Secondary Efficacy Analyses

Objective: To evaluate the proportion of days during pollen season for which active patients experience a lower TCS than placebo patients.

Endpoint: The percentage of days during peak pollen season for which the group average TCS score was lower in the immunotherapy group versus placebo control.

Statistical Analysis Plan

Population: The per protocol dataset.

Analysis Period: The analysis period will be peak mountain cedar pollen season in the local area, defined as the period when the first cedar pollen count was above 100 ppm to the last date pollen was above 100 ppm followed by more than five (5) consecutive days with a count below 100 ppm.

Statistical Testing Method and Considerations: The Clopper-Pearson binomial exact test of difference of proportions will be used for this comparison using the Holm-Bonferroni correction for multiple tests due to correlation between endpoints based on the same underlying TCS data.

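### The SAP runs the primary and secondary efficacy tests on the per-protocol set, although Protocol 9.3 and SAP 6 give efficacy tables to MITT and only supplementary ones to PP

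*SAP*

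**What the plan says.** **Population for the tests.** SAP 9.1 (primary, average daily TCS) specifies "The per protocol dataset, which includes participants who received three study treatment injections and completed at least 50% of expected electronic diary responses", with no major protocol violations. SAP 9.2 (proportion of days with lower TCS) states "Population: The per protocol dataset". The analyses in SAP 9.3 for which a population is given also use PP.

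**Roles of the sets.** SAP 6 defines MITT as patients with at least one injection who "completed at least one (1) complete daily e-diary assessment and be used for production of efficacy tables". It says of PP that it "will be used for production of supplementary efficacy tables and analyses". Protocol 9.3 assigns the same two roles. Protocol 9.4.2, which describes the primary efficacy analysis, names no population.

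**Diary threshold for PP.** SAP 6 requires that patients "completed at least one e-diary responses during the allergy season (defined below), and had no other major protocol violations". Protocol 9.3 requires that they "completed at least 50% of e-diary responses during the allergy season (follow-up period"). Protocol 8.1.1.5 uses the same level: "Patients will be considered compliance if they complete at least 50% of expected daily responses".

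**Follow-up of patients outside PP.** Protocol 7.1 says "Discontinuation of ILIT treatment does not mean discontinuation from the study, and remaining study procedures should be completed". Protocol 6.4 says that injected patients are not withdrawn for poor diary compliance. Protocol 7.2 permits withdrawal for significant non-compliance but does not require it.

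**The concern.** PP membership depends on receiving all three injections, completing the diary and having no major violation. All of these are settled after randomisation. If exclusion is related to TCS and differs between arms, the primary comparison is biased. If it is unrelated to TCS, the trial only loses power. Either way, data that the protocol sets out to collect are left out of a superiority test, and no imputation is planned to bring them back.

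Differential exclusion is possible but not established. Protocol 6.3 says that reactions were less frequent on placebo in previous immunotherapy trials. The ILIT studies in Protocol 2.2 are mixed: in one, an active patient dropped out after a local reaction; in another, all 15 patients completed their injections; in a third, more adverse events were reported on placebo. Diary completion may also depend on symptoms, in either direction.

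SAP 6 allows descriptive MITT efficacy tables, and disposition tables and a deviation listing are planned, so some check exists. The hypothesis tests themselves have no MITT counterpart. The safety analysis uses the Safety set and is unaffected.

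**Working it through.** **1. Which text governs.** SAP 1 says that SAP definitions prevail over the protocol. That does not settle the matter, because SAP 6 conflicts with SAP 9.1 and 9.2 inside the SAP. SAP 1 also says that discrepancies with the protocol will be described, and this one is not.

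**2. Which PP definition applies.** SAP 9.1 states 50%, so the primary test is settled and agrees with Protocol 9.3 and 8.1.1.5. SAP 9.2 and 9.3 state no threshold, so one response (SAP 6) or 50% (SAP 9.1) could be meant.

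**3. The plan's own sample size.** Inputs from Protocol 9.2 and SAP 5.1: f² = 0.50, two predictors, α = 0.05, power 80%. The overall F test has 2 and N − 3 degrees of freedom and noncentrality f²N. The smallest N with power of at least 0.80 is 23 (noncentrality 0.50 × 23 = 11.5, power 0.810), which matches the plan. It contains no allowance for exclusion from PP.

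**4. Bias and type I error.** Inputs: SD 9.0 (SAP 5.1), no true effect, 23 patients split 12 ILIT and 11 placebo, two-sided t test at 0.05. The number excluded (k) and the correlation ρ with TCS are assumed. Each patient has an exclusion score of ±ρ × (standardised TCS) + √(1 − ρ²) × noise, and the k highest are removed. There were 200,000 simulated trials per scenario.

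| ILIT-only exclusions, k = 1 / 2 / 3 | Bias in points | Type I error |
|---|---|---|
| ρ = 0 | 0 / 0 / 0 | 5.0 / 5.0 / 5.0% |
| ρ = 0.3 | 0.4 / 0.7 / 1.1 | 5.2 / 5.4 / 5.9% |
| ρ = 0.5 | 0.7 / 1.2 / 1.8 | 5.5 / 6.3 / 7.4% |

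The bias favours ILIT if high scorers are lost and goes against ILIT by the same amount if low scorers are lost. At ρ = 0.5, two exclusions per arm in the same direction give 0.1 points and 5.6%; in opposite directions they give 2.6 points and 10%. For scale, SAP 5.2 cites a 1.5-point TCS difference as the basis for approval of an oral grass-pollen product.

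**5. Power if exclusion is unrelated to TCS.** Two-sample t test, difference 8.0, SD 9.0, noncentrality 8 / (9√(1/n₁ + 1/n₂)).

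- 12 vs 11: noncentrality 2.13, power 0.529. At 10 vs 9: 1.93, power 0.446. Drop 0.083.
- 16 vs 16: noncentrality 2.51, power 0.682. At 14 vs 14: 2.35, power 0.620. Drop 0.062.

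Only the drop belongs to this point. The starting level is a separate sample-size question. On the plan's own F-test basis, losing four patients takes 23 to 19 (0.810 to 0.708) or 32 to 28 (0.935 to 0.893), a loss of 10 or 4 percentage points.

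**6. Two minor inconsistencies.** SAP 6 counts days at or above 100 and ends the season with five days below. SAP 9.1 and 9.2 require counts above 100 and more than five days below. The rules differ for a count of exactly 100 and for a lull of exactly five days. SAP 6 also leaves open whether the first or the last qualifying date ends the season. In an invented series (20 days at 500, 6 at 60, 25 at 500, then low) the window is 20 days if the first date is meant, and 20 + 6 + 25 = 51 days under SAP 9.1. Separately, SAP 9.3 analyses NRS-11 pain in PP, although both documents give tolerability tables to the Safety set.

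**The case against.** The trial is a phase 2 proof-of-concept study. Protocol 9.4.2 makes efficacy secondary to safety, Protocol 9.4.1 claims the flexibility of an exploratory trial, and neither document uses the term primary analysis population. This lowers the stakes but does not remove the conflict: calling PP output supplementary makes MITT the main efficacy set, and SAP 6.7 makes the secondary tests conditional on the primary TCS result.

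The harm is hypothetical. No exclusion rate or link with TCS is given, and the 10% error needs exclusions in opposite directions in the two arms, which nothing in the documents supports. That is correct. The case rests on the contradiction and the missing MITT test, not on demonstrated bias.

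The 50% rule has a rationale, since both sample-size sections assume TCS on at least half of the days. MITT admits patients with a single diary day and still conditions on that day. This stands, and it is why a supportive PP analysis and a sensitivity analysis are needed.

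Reading 50% forward from SAP 9.1 into 9.2 is natural, but SAP 6 says otherwise. The season rule and the pain population are separate matters and add nothing to the weight of the main point.

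**Conclusion.** The plan is wrong as written. The population determines the primary p-value, the SAP contradicts itself and the protocol on it, and the set chosen for testing is the one more exposed to selection. This should be corrected before the tests are run.

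The size is unknown in amount and direction. On the assumed scenarios with ILIT-only exclusions, the bias runs from nil to about 1.8 points and the type I error from 5.0% to 7.4%. If exclusion is unrelated to TCS, the cost is 6 to 8 percentage points of power for two exclusions per arm on the t-test basis. The textual conflict does not depend on any of these assumptions.

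**What to change.** In SAP 9.1 and 9.2, name MITT as the population for the efficacy tests: at least one injection and at least one in-season diary day, analysed as randomised. The in-season condition is a small addition to SAP 6. Keep PP as supportive, with one 50% threshold throughout the SAP. Tabulate numbers and reasons for PP exclusion by arm, building on the planned disposition tables and deviation listing (SAP 7.1 Subject Disposition and 8.2). Because one diary day would count as much as a full season, add an analysis weighted by diary days or a repeated-measures model.

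As minor corrections, write one season rule in SAP 6, 9.1 and 9.2, for example from the first day at or above 100 to the last such day followed by at least five consecutive days below 100. Analyse NRS-11 pain in the Safety set. Make all these choices without reference to unblinded results.

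The cost is wording and some programming, with no new data. Power can move either way. Suppose MITT retains two ILIT patients whom PP would exclude, with full diaries:

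| Share of the effect they have | 12 vs 11 | 16 vs 16 |
|---|---|---|
| All | 0.53 | 0.68 |
| Half | 0.45 | 0.62 |
| None | 0.37 | 0.55 |
| PP, two lost per arm | 0.45 | 0.62 |
| PP, two lost from ILIT only | 0.49 | 0.65 |

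Break-even is about half the effect if PP loses two per arm, and about 70 to 75% of it if PP loses ILIT patients only. If two patients per arm have a single diary day, power at 12 vs 11 with full effect is 0.48 to 0.52 (assumed day-to-day SD 8 to 4, 60-day season).

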9.2 Secondary Efficacy Analyses

Objective: To evaluate the proportion of days during pollen season for which active patients experience a lower TCS than placebo patients.

Endpoint: The percentage of days during peak pollen season for which the group average TCS score was lower in the immunotherapy group versus placebo control.

Statistical Analysis Plan

Population: The per protocol dataset.

Analysis Period: The analysis period will be peak mountain cedar pollen season in the local area, defined as the period when the first cedar pollen count was above 100 ppm to the last date pollen was above 100 ppm followed by more than five (5) consecutive days with a count below 100 ppm.

Statistical Testing Method and Considerations: The Clopper-Pearson binomial exact test of difference of proportions will be used for this comparison using the Holm-Bonferroni correction for multiple tests due to correlation between endpoints based on the same underlying TCS data.

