#### 9.4.3 ANALYSIS OF ADDITIONAL SECONDARY EFFICACY ENDPOINT(S)

Secondary efficacy criteria will be compared between treatment groups using appropriate methods according to their nominal or quantitative nature. Specifically, the percentage of days for which the TCS is lower will be assessed using the  $\chi^2$  test, while the NRS-11 and immunologic response will be analyzed using the Mann-Whitney test. Treatment satisfaction may be presented as a dichotomized variable, in which case it will be analyzed using a paired samples t-test. Co-variates will be assessed using a regression model for ordinal data. Data will be presented in the form of descriptive statistics and appropriate tables and graphs with a conclusion on whether or not the significance level allowed the null hypothesis for each test to be rejected.

---

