6.7 Multiplicity

There is a single primary endpoint, with a single primary hypothesis test, so no adjustment for multiplicity is needed for the primary endpoint.

To adjust for multiplicity among the secondary endpoints, a fixed testing order will be used. The secondary endpoints will be tested in the pre-specified order, if the primary endpoint is found to be statistically significant. Testing will proceed to the next endpoint if the preceding endpoint is found to be statistically significant at the 5% (two-sided) level. The moment an endpoint is found not to be significant at the 5% (two-sided) level, all remaining endpoints will be considered exploratory, instead of confirmatory. No adjustment for multiplicity will be made for the exploratory endpoints.

The Holm-Bonferroni correction will be used for pre-specified multiple comparisons due to correlation between endpoints based on the TCS.

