7. DATA HANDLING METHODS

7.1 Missing Data

No imputations for missing days of diary.

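### SAP 9.2 tests the share of days with a lower ILIT mean TCS as if days were independent, so its nominal p-value is not valid; a minor separate slip is the paired t-test for the yes/no PEQ item in SAP 9.3

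*SAP*

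**What the plan says.** SAP 9.2 defines the endpoint as the percentage of peak-season days on which "the group average TCS score was lower in the immunotherapy group versus placebo control". On the method it says: "The Clopper-Pearson binomial exact test of difference of proportions will be used for this comparison". It adds a Holm-Bonferroni correction because endpoints share the same TCS data. Protocol 9.4.3 has a different test with the same unit: "the percentage of days for which the TCS is lower will be assessed using the" chi-square test. Neither names a patient-level method for this endpoint or gives a null value.

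For the primary endpoint the SAP does recognise the data structure: "The TCS is a repeated measure, but statistical comparisons were between group average TCS scores during peak season" (SAP 9.1). On the gate, SAP 6.7 says: "The secondary endpoints will be tested in the pre-specified order, if the primary endpoint is found to be statistically significant". SAP 6.6 adds that p-values will be reported.

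On diaries, SAP 7.1 says "No imputations for missing days of diary". The per-protocol set used in 9.2 needs patients who "completed at least 50% of expected electronic diary responses during the allergy season" according to SAP 9.1, but who "completed at least one e-diary responses during the allergy season" according to SAP 6.

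For the PEQ satisfaction item, SAP 9.3 item 2 and protocol 9.4.3 both specify a paired-samples t-test. SAP 9.3 calls the item dichotomous and the comparison between-group. The trial is parallel-group (SAP 4).

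**The concern.** Each day yields one comparison of two group means, and the same patients supply those means throughout the season. If one small arm happens to contain less symptomatic patients, its mean tends to be lower on most days with no treatment effect at all. An exact binomial or chi-square test reads that single chance imbalance as many separate pieces of evidence. The Holm-Bonferroni wording deals with correlation between endpoints and does nothing about correlation between days.

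The method is also not executable as worded. The ILIT-lower share and the placebo-lower share are complements on the same days, so there are not two proportions to compare.

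At stake is a nominal p-value for the first secondary endpoint that can look decisive in either direction without any treatment effect. For the PEQ item, no pairs exist by design, so the named test either cannot be run or depends on how the rows are sorted.

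**Working it through.** **Inputs from the documents.** 23 enrolled (SAP 5.1), taken as 12 v 11; 32 as target (protocol 5.4), taken as 16 v 16; two-sided 5% level (SAP 6.7). The plan gives no operating figure for this endpoint. Its primary-endpoint N of 23 does reproduce: a noncentral F test with two predictors and noncentrality 0.50 × 23 = 11.5 gives power 0.810.

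**Assumed inputs, because the plan states none.** Null share 0.5; season 30 to 90 days (78 is the season length of the US grass-pollen ILIT trial described in protocol 2.2); within-patient correlation (ICC) 0.1 to 0.9; lag-1 correlation of daily errors 0 or 0.5; 0 to 50% of diary days missing at random.

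**Step 1: complete diaries, constant within-patient correlation.** Let D be the daily difference in group means, with between-patient variance B and within-patient variance W.
- Variance of D = (B + W)(1/n1 + 1/n2).
- Covariance of D between two days = B(1/n1 + 1/n2).
- The correlation between days is therefore B/(B + W) = ICC, whatever the arm sizes.

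Given a persistent imbalance z (standard normal), the chance that ILIT is lower on a day is Φ(z√(ICC/(1 − ICC))). With K days, the exact test rejects when the count is at least c or at most K − c, where c is the smallest count with 2·P(X ≥ c | K, 0.5) ≤ 0.05. Integrating over z gives the null rejection rate:

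| K | c | ICC 0 | ICC 0.1 | ICC 0.3 | ICC 0.5 |
|---|---|---|---|---|---|
| 30 | 21 | 4.3% | 24.7% | 49.7% | 64.5% |
| 60 | 39 | 2.7% | 33.1% | 59.2% | 72.1% |
| 78 | 49 | 3.1% | 39.4% | 64.4% | 75.9% |
| 90 | 55 | 4.5% | 45.7% | 68.9% | 79.1% |

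Hand check for 78 days and ICC 0.5: the test needs a share of 49/78 = 0.628. Φ(z) exceeds 0.628 when z > 0.327, and P(|Z| > 0.327) = 0.744, close to the 75.9% in the table.

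**Step 2: simulation with missing diaries and serial correlation.** 144 scenarios (12 v 11 or 16 v 16; 30 or 78 days), 2,000 null trials each, normal scores:
- Day-level test rejects: 14.8 to 91.8%. Rejections favouring ILIT: 7.0 to 46.0% of trials, about half of all rejections.
- Central example (16 v 16, 78 days, ICC 0.5, lag-1 correlation 0.5, 25% missing): 69.8%, of which 35.6 points favour ILIT.
- Lowest (12 v 11, 30 days, ICC 0.1, lag-1 correlation 0, 50% missing): 14.8%.
- Truly independent days: 2.6 to 4.8%.
- t-test on one season mean per patient: 3.6 to 6.4%.
- Both tests significant, as the fixed order requires: 3.6 to 6.4%.
- Days test significant when the patient-mean test is falsely significant: 75.7 to 100%.

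With 75% of diary days missing, which the SAP 6 wording allows and the SAP 9.1 wording does not, the day-level test rejects in 6.9 to 57.8%.

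**Step 3: reading the test as two proportions.** Comparing the ILIT-lower share with its complement as if they were two samples of 60 days rejects in 15.5% of null trials even when days are independent.

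**Step 4: PEQ item, illustrative data of 14/16 v 9/16 satisfied.** Pair the rows arbitrarily. Let b be pairs with ILIT yes and placebo no, and c the reverse. Then b − c = 14 − 9 = 5, and c can only be 0, 1 or 2 because two ILIT patients said no. The mean difference is always 5/16 = 0.3125, with s² = (b + c − 16 × 0.3125²)/15.
- c = 0, b = 5: s² = (5 − 1.5625)/15 = 0.229; t = 0.3125/√(0.229/16) = 2.61; p = 0.020.
- c = 2, b = 7: s² = (9 − 1.5625)/15 = 0.496; t = 0.3125/√(0.496/16) = 1.78; p = 0.096.

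Fisher's exact p is 0.113 whatever the row order. With 12 v 11 the paired routine returns an error.

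**The case against.** The strongest reply is that little rides on this p-value. The trial is an exploratory proof of concept, SAP 6.7 tests secondaries only after a significant primary, and protocol 9.4.1 promises alternative tests when assumptions fail. The gating argument largely stands. A reader might infer that the trial's false-claim rate rises to 15 to 92%. The documents do not support that, because the day-level test is confirmatory only behind the primary. Nor does the Holm wording in SAP 6.7 say that it replaces the gate.

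The gate figures do assume that SAP 9.1 compares one season mean per patient. SAP 9.1 speaks of group averages tested by ANOVA or Kruskal-Wallis and does not say this. Protocol 9.4.1 is general and names neither this test nor a substitute.

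It is also fair that the range of rejection rates is wide and rests on unstated correlations and on normal scores. The TCS is bounded (6 × 3 + 6 + 6 + 8 = 38) and moves in steps. These are scenario results, not bounds, but the excess appears at every positive ICC tried.

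A reader might infer that the endpoint itself is meaningless. It is not: the percentage of days remains a valid description, and only the p-value or interval fails. Likewise the PEQ slip does not spoil all of the satisfaction analysis, since SAP 9.3 gives the PGI-I a Wilcoxon rank sum test. SAP 9.3 files the PEQ item as exploratory, although SAP 2.3 lists satisfaction as a secondary.

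**Conclusion.** The concern holds for the inference in SAP 9.2, not for the description. With no treatment effect, the day-level test rejects in about 15 to 92% of trials at a nominal 5% in the scenarios tried (null share 0.5, 23 to 32 patients, 30 to 78 days, ICC 0.1 to 0.9, up to half of diary days missing), and in about 70% in the central example. Provided SAP 9.1 means one season mean per patient, false confirmatory claims stay near 5%. The day-level test then adds little confirmation, because it usually repeats a false primary result. The harm is a misleading nominal p-value for the first secondary. This should be fixed, but it is not a threat to the primary analysis on that reading.

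The paired t-test for the PEQ item is wrong as written but of minor consequence. The 14/16 v 9/16 data are illustrative.

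**What to change.** - **SAP 9.2:** report the percentage of days descriptively, with no binomial or chi-square p-value, and rely on the patient-level TCS comparison for inference.
- **SAP 6.7:** state the consequence. SAP 9.3 already treats the other secondaries as exploratory, so no secondary is then tested confirmatorily, and the fixed order and the Holm wording no longer apply to 9.2.
- **If a p-value is still wanted:** permute whole patients between arms and recompute the day count. Null rejection was 0 to 5% in nine scenarios. Ties can leave this test with little or no power when the day share saturates. Under the plan's own effect (8.0 with SD 9.0), 30 days and complete diaries, rough runs of 200 trials gave about 4% power at ICC 0.5 and 0% at ICC 0.7 and 0.9, against roughly 50 to 70% for a t-test on patient means. Power recovers to around half with 78 days, 25% missing and ICC 0.5.
- **SAP 9.3 item 2:** use Fisher's exact test for the PEQ item, with a confidence interval for the difference in proportions.
- **Record both changes** in the SAP as departures from protocol 9.4.3, with their timing relative to unblinding. SAP 6.2 shows that the SAP was written after enrolment.

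The cost is that the first secondary loses its p-value and the trial has no confirmatory secondary. Otherwise only SAP wording and a few lines of code change.
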